5.6 Study Data

Study data for all qualified patients will be collected and stored on a proprietary data platform that has been tested and validated by a HIPAA compliant review system. This platform provides for role-based accountability. The platform is called the National Medication Safety, Outcomes and Adherence Platform (NMSOAP). The data collection for all study participants that receive AZD7442 treatment will include: one baseline Experience/COA survey, one baseline QoL assessment, 14 follow-up Experience/COA surveys, 5 follow-up QoL assessments, at least 5 serum concentrations of AZD7442, at least 5 SARS-CoV-2 RBD-IgG antibody levels, and at least 2 CD4/CD8 measurements. An additional AZD7442 serum concentration, SARS-CoV-2 RBD-IgG antibody level and CD4/CD8 assay will be performed if a symptomatic patient becomes SARS-CoV-2 RNA by RT-PCR COVID-19 positive. In this case, additional medical records will be obtained. These could include unplanned telehealth visit, Urgent Care/ER visit or hospitalization, pharmacy data and medical insurance claims data.

6.0 Sites, Subjects Stratification
	
6.1 Sites The study will be conducted at up to 75 hematology/oncology medical practice locations nationally.
 
6.2 Subjects The program will enroll approximately 1,500 qualified patients divided into approximately 1,200 qualified solid tumor and approximately 300 qualified hematologic malignancy patients either on active therapy or treated within the past 12 months.
 
6.3 Stratification Qualified solid tumor and hematologic malignancy patients will be stratified based on current or former treatment with chemotherapy only, immunotherapy only, targeted therapy only, or other therapy/combination therapy only and sub-stratified by: currently on active treatment, ≤3 months post-treatment or >3 months and ≤12 months post-treatment.

7.0 Study Duration
	
 ➤ Enrollment: Approximately 3 months ➤ Patient Follow-Up: 12 months from date of enrollment

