
15.0 Interim Analysis
	
the analysis will determine which group is more likely to experience such infections.
 
An interim analysis will be performed after the first 6-month assessments are completed for the first 50% of the targeted patient sample for each malignancy, i.e., 750 patients including 600 solid tumor and 150 hematologic malignancies. The primary endpoint of the interim analysis will be the serum concentration of AZD7442 for all patients with comparisons between disease categories.
 
Secondary analyses will be conducted on the following measures in all patients included in the interim analysis set:
 
 • Incidence of break-through infections in all patients and then sub-divided into solid tumor and hematologic malignancy. • Time to infection compared between solid tumor and hematologic malignancy • RBD-IgG levels for all patients with comparisons between disease category • CD4/CD8 levels for all patients with comparisons between disease category

16.0 Immunological Sub-Study Endpoints
	
16.1 Immunologic Sub-Study Endpoints
 
 • Comparison of CD4 T-cell and CD8 T-cell function in all cancer patients at 30 days post initial administration of AZD7442 to similar tests performed in normal healthy donor subjects • Comparison of the relationship between different cancer treatment regimens and T-cell function in all cancer patients at 30 days post administration of AZD7442 • Comparison of the relationship between type of cancer (solid vs. hematologic) and T-cell function in all patients at 30 days post administration of AZD7442 • Comparison of the immunologic profile relating to AZD7442 serum level and T-cell function at the time of PCR positive SARS-CoV-2 infection in all cancer patients to Day 30 T-cell functionality • Comparison of the relationship between change from Day 30 in AZD7442 serum level, T- cell function and World Health Organization Ordinal Scale

	
(WOS) for SARS-CoV-2 disease severity in all cancer patients with documented PCR positive SARS-CoV-2 infection
 
 • Comparison of the relationship between change from Day 30 in AZD7442 serum level, T- cell function and World Health Organization Ordinal Scale (WOS) for SARS-CoV-2 disease severity in all cancer patients with documented RT-PCR positive SARS-CoV-2 infection based on type of cancer treatment.

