
17.0 Statistical Considerations
	
17.1 Sample Size Estimation
 
This program will recruit approximately 1,500 treated cancer patients divided into approximately 1,200 qualified solid tumor and 300 qualified hematologic malignancy patients from approximately 75 hematology/oncology medical practice locations throughout the United States. It is expected that on average, each site will enroll 16 solid tumor and 4 hematologic malignancy patients.
 
17.2 Sample Size Power
 
With a sample size of 1500 patients, the power to detect a non-inferiority margin of 5 mcg/ml with a standard deviation of 25 mcg/ml and Type I error rate of 1% is estimated to be approximately 80% when comparing the serum concentration levels between solid tumor and hematologic malignancy groups. The assumed comparison is between 1200 solid tumor and 300 hematologic malignancy patients. A target sample of 1500 patients will provide adequate size to analyze all of the secondary endpoints identified in the baseline and follow-up patient experience/COA surveys and the QoL surveys.
 
At the time of interim analysis, the power to detect a 5 mcg/ml non-inferiority margin with a standard deviation of 25 mcg/ml and Type I error rate of 1% is estimated to be approximately 45%. This assumes a sample of 600 solid tumor and 150 hematologic malignancy patients.
 
17.3 Stratification
 
This is an open-label, pragmatic, multi-center study of participants receiving AZD7442 600 mg IM or IV for prevention of symptomatic SARS-CoV-2 infection including SARS-CoV-2 related hospitalization and/or SARS-CoV-2 related death.

Patients will be stratified based on type of cancer (solid tumor vs hematologic malignancy) with additional stratification for concomitant treatment regimen of chemotherapy only, immunotherapy only, targeted therapy only and other therapy/combination therapy. It is assumed that 80% of enrolled cancer patients will have solid tumors. Patients will be sub-stratified by: currently on active treatment, ≤ 3 months post-treatment or > 3 months and ≤ 12 months post-treatment.

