	
data to establish a standardized assessment of SARS-CoV-2 disease severity using the World Health Organization Ordinal Scale (WOS).
 
In SARS-COV-2 RNA by RT-PCR positive symptomatic SARS-CoV-2 patients, the WOS associated with the time of T-cell function blood draw will be determined by the CEC using manual review. The data to be evaluated using the patient’s electronic health record (EHR) and other available information will include the components required to determine the World Health Organization Ordinal Scale (WOS).

21.0 Data Monitoring Committee (DMC)
	
21.1 Data Monitoring Committee
 
A Data Monitoring Committee (DMC) will be established for the interim analysis. The DMC will be unblinded to therapy in this open-label study. It will oversee the study with primary responsibility for ensuring that all data meet regulatory standards for the goals and objectives of the interim analysis. Specific goals and responsibilities of the DMC include the following:
 
 • Oversight of the study with primary responsibility for review of all data generated for the interim analysis • Review of adverse event data as part of the interim analysis with special attention to the incidence of SARS-CoV-2 by RT-PCR positive patients • Conduct of the planned interim analysis including DMC recommendations relating to potential AZD7442 redosing.

22.0. Machine Learning
	
22.1 Machine Learning Application
 
Machine Learning will be applied in order to predict the incidence of SARS-CoV-2 infection based on the serum concentration of AZD7442 at Days 30, 90, 180, 270 and 360 post-baseline for solid tumor and hematologic malignancy patients.
 
Machine Learning will be used to integrate the data from Patient Experience/ COA and QoL surveys with medical records, pharmacy fill/refill and medical insurance claims data for all patients.

SUPPLEMENTAL INFORMATION

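### The interim infection analyses use only the first 750 patients although, on the planned enrollment, all 1,500 will have been dosed, and the patient set for the DMC's adverse event review is not stated

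*Protocol*

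**What the plan says.** Protocol section 15.1 sets the trigger: "An interim analysis will be performed after the first 6-month assessments are completed for the first 50% of the targeted patient sample for each malignancy", that is, "750 patients including 600 solid tumor and 150 hematologic malignancies". The stated purpose is to learn whether infection is prevented in the first 6 months and which malignancy group has more break-throughs. Serum concentration is the interim's primary endpoint. The other measures are introduced by "Secondary analyses will be conducted on the following measures in all patients included in the interim analysis set". They are break-through infections, time to infection, RBD-IgG and CD4/CD8. Adverse events are not on that list.

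Section 17.2 uses the same set for the interim power: "This assumes a sample of 600 solid tumor and 150 hematologic malignancy patients".

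Section 7.0 gives the accrual plan: "Enrollment: Approximately 3 months", with 12 months of follow-up per patient.

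Section 21.1 creates the DMC for the interim analysis. One of its tasks is "Review of adverse event data as part of the interim analysis with special attention to the incidence of SARS-CoV-2 by RT-PCR positive patients". The section names no patient set for that task and no other DMC data review. It does give the DMC general oversight of the study, and it asks for recommendations on possible redosing.

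**The concern.** The number 750 suits the concentration comparison, which needs a Day 180 sample. Infection is different: every dosed patient contributes information from the day of dosing. If enrollment really takes about 3 months, nobody is still waiting to be dosed when the interim falls due, and the second 750 patients have been followed for most of the 6-month period that the interim asks about. Section 15.1 leaves their infections out.

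The loss is greatest where patients are fewest. The hematologic estimate uses 150 patients when 300 have been dosed.

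The same interim is the only data review that section 21.1 gives the DMC. Whether its adverse event review covers 750 or 1,500 patients is left open. Section 9.3 schedules the second dose at Day 180, so the patients who have not reached that visit at the cut-off are essentially the second 750. The DMC is asked about redosing while the infection analyses before it exclude those patients. This is a mismatch of scope between sections; no view on redosing is implied.

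**Working it through.** **Plan's own figure.** Section 17.2 gives about 45% interim power for a margin of 5 mcg/ml, SD 25, type I error 1%, 600 vs 150. The standard error is 25 × √(1/600 + 1/150) = 2.282, and 5/2.282 = 2.191. One-sided 1% power is Φ(2.191 − 2.326) = 44.6%, which reproduces the figure. It confirms that the interim set is the 750. This power concerns concentrations only and does not change under the fix below.

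**Timing.** Enrollment of E months is taken from section 7.0. Even accrual is an assumption; the Protocol gives no accrual shape.
- Cut-off: T = E/2 + 6. For E = 3, T = 7.5 months.
- Follow-up of the last patient: T − E = 4.5 months (4.3 to 4.6 with the ±5-day visit window).
- Mean follow-up of the first 750: T − E/4 = 6.75 months, so 750 × 6.75 = 5,062 patient-months.
- Mean follow-up of the other 750: T − 3E/4 = 5.25 months, so 750 × 5.25 = 3,938 patient-months.

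**Share of follow-up not used.**
- All accrued follow-up: 3,938/9,000 = 43.8%.
- First 750 capped at 6 months: 3,938/(4,500 + 3,938) = 46.7%.

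**Sensitivity (before dropout).**

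| Enrollment (even) | Last patient's follow-up | Not used, all accrued | Not used, capped at 6 months |
|---|---|---|---|
| 3 months | 4.5 months | 43.8% | 46.7% |
| 6 months | 3.0 months | 37.5% | 42.9% |
| 9 months | 1.5 months | 31.3% | 38.5% |
| 12 months | 0 months | 25.0% | 33.3% |

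Within a 3-month enrollment, strongly front-loaded accrual gives the last patient 3.75 months and back-loaded accrual up to 5.4 months. The unused share of all accrued follow-up runs from 43% to 46%.

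**Hematologic precision.** Weighting the second 150 by 5.25/6 gives 150 + 131 = 281 patient-equivalents. Confidence interval half-widths scale by √(150/281) = 0.73. For assumed 6-month infection risks of 5%, 10% and 15% (the Protocol gives none), the 95% half-width falls from 3.5, 4.8 and 5.7 points to about 2.5, 3.5 and 4.2 points.

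**DMC safety review, only if it is read as covering the 750.** All patients together make 750 + 750 × 5.25/6 = 1,406 patient-equivalents.
- For an illustrative 6-month risk of 0.2% (an assumption), the chance of at least one case is 1 − 0.998^750 = 78%, against 1 − 0.998^1,406 = 94%.
- At 0.1% the pair is 53% and 76%. At 0.5% it is 98% and over 99%.
- With no cases, the upper 95% bound 1 − 0.05^(1/n) is 0.40% against 0.21% overall, and 2.0% against 1.1% in hematologic patients.

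**The case against.** Restricting the infection analyses to the 750 can be defended. Those patients have the full 6-month window, and the others mostly do not. One fixed set keeps concentration, antibody, T-cell and infection results in the same people. Section 15.1 states no infection-based stopping boundary that a smaller set would weaken. This stands as far as it goes: the choice is not an error. It does not make the restriction necessary, because a time-to-event analysis with censoring at the cut-off handles 4.5 to 6 months of follow-up without difficulty.

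Four stronger readings are tempting, and the Protocol does not support them.
- A reader might infer that the DMC's adverse event review is limited to the 750. Section 21.1 fixes its occasion, not its patients, and a charter or SAP that is not shown may settle the listings.
- A reader might infer that nobody looks at safety in the other 750. Sections 18.5, 18.7 and 25.8 say otherwise. Pharmacovigilance oversees all safety data, SAEs are due within 24 hours, and acute-illness admissions go to the CEC. Nor are the later patients' infection data lost to the study, because the final analysis under section 17.6 is not limited to the interim set.
- A reader might infer that half the patients means half the chance of seeing a rare harm. It means roughly half the expected cases. At the illustrative 0.2% risk the chances are 78% and 94%.
- A reader might infer that patients who died or withdrew before Day 180 are removed. The wording "first 6-month assessments are completed for the first 50% of the targeted patient sample for each malignancy" governs when the interim happens and does not say this. It is loose enough to be worth tightening.

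**Conclusion.** The point holds as an inexpensive improvement to the interim, together with one clarification. On the Protocol's 3-month enrollment and even accrual, section 15.1 sets aside about 44% to 47% of the infection follow-up available at the cut-off, on the question the interim is meant to answer. It also rests hematologic precision on 150 rather than 300 patients. The gain shrinks if enrollment is slower: 38% of all accrued follow-up at 6 months and 31% at 9. Beyond 12 months not all 1,500 would yet be dosed.

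On safety, the finding is narrower. The DMC's only named data review has no stated patient set. Oversight of all patients exists elsewhere, so the gap lies in the DMC's remit and not in safety monitoring as a whole.

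**What to change.** - **Section 15.1:** keep the concentration, RBD-IgG and T-cell comparisons in the first 600 solid tumor and 150 hematologic patients, defined by order of dosing, so that early deaths and withdrawals stay counted in the set.
- **Section 15.1:** run infection incidence and time to infection in every patient who has received any AZD7442 by the data cut-off, censored there. Because follow-up is unequal, report incidence per person-time or as a Kaplan–Meier estimate, not as a raw proportion.
- **Section 21.1:** state that the DMC's review of AEs, SAEs, AESIs and deaths covers the same all-dosed set.
- **Section 17.4:** name that all-dosed set. The ITT population will not serve, since it requires the Day 30 T-cell assay and a post-baseline RBD-IgG, first routinely drawn at Day 90.

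The cost is wording in these sections and interim cleaning of infection and safety variables for about 750 more patients. No new visits, samples or patients are needed, and the interim concentration comparison and its stated power are unaffected.

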17.4 Populations for Analysis

The study will analyze two populations as defined by Intent-To-Treat (ITT) and Per Protocol (PP) criteria.

- The ITT population includes all participants who complete enrollment, complete the baseline Patient Experience/COA survey, baseline QoL assessment, baseline SARS-CoV-2 RBD-IgG, undergo AZD7442 600 mg IM or IV administration, complete at least one serum concentration AZD7442 measurement post-baseline AZD7442 administration, one RBD-IgG post-baseline, complete the Day 30 T-Cell assay, complete at least one follow-up Patient Experience/COA survey and one QoL assessment.
- The PP population includes all participants who complete all AZD7442 600 mg IM or IV administrations, complete the baseline Patient Experience/COA surveys, complete the baseline QoL assessment, complete the baseline SARS-CoV-2 RBD-IgG antibody level, complete the Day 30 and Day 210 T-Cell assay, complete 75% of follow-up Patient Experience/COA surveys, 75% of QoL assessments, 75% of RBD-IgG antibody levels and 75% of serum concentration of AZD7442 measurements post-baseline AZD7442 administration.

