- On active treatment with high-dose corticosteroids (i.e., ≥ 20 mg prednisone or equivalent per day when administered for ≥ 2 weeks), as well as any FDA approved alkylating agents, antimetabolites, transplant-related immunosuppressive drugs, cancer chemotherapeutic agents classified as severely immunosuppressive, tumor-necrosis (TNF) blockers, and other biologic agents that are immunosuppressive or immunomodulatory (e.g., B-cell depleting agents) or any combination of these agents.
- Previously treated but not on active treatment as defined in Section 8.1.

The patient's clinical stability will be defined by the Investigator at the time of enrollment and applies to all solid tumor or hematologic malignancy patients. The categories for clinical stability are: (1) in remission, (2) stable or (3) progressing. These assessments of clinical stability will be repeated at month 3 and month 6 of patient follow-up. Hematologic malignancy patients may be enrolled even if their therapy is completed and their cancer status is considered stable or in remission. Solid tumor patients are excluded if their therapy has been completed more than 6 months prior to baseline and their cancer is either stable or in remission. All solid tumor or hematologic malignancy patients may be enrolled if their cancer status is considered as progressing, whether or not they are on active treatment. Enrolled patients will also fulfill one of the following criteria: (1) they have received any SARS-CoV-2 vaccination with an FDA EUA vaccine (Janssen, Moderna or Pfizer) and do not wish to receive an additional vaccine dose, or (2) they have received any SARS-CoV-2 vaccination with an FDA EUA vaccine (Janssen, Moderna or Pfizer) and wish to receive an additional Janssen, Moderna, Pfizer vaccine dose.

The baseline evaluation will require SARS-CoV-2 specific RBD-IgG antibody testing in all vaccinated participants who are at least 4 weeks post their most recent vaccine dose. To qualify for enrollment into the program, each solid tumor cancer patient must be either on active treatment, up to 6 months post-treatment and/or has progression of his/her cancer. Hematologic malignancy patients may be enrolled on active treatment or up to 12 months post- treatment and if their cancer is in remission, stable or progressing.

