- For patients not on active oral, IM or IV therapy at the time of enrollment, previous treatments may have been initiated at any time prior to treatment inactivity but must meet the hematologic or solid tumor post treatment requirements stated above
- Concomitant radiation therapy is permitted but cannot be the sole therapy
- Have been vaccinated with one or more doses of Janssen, Moderna or Pfizer COVID-19 vaccine at least 14 days prior to Baseline

- If having been previously diagnosed with SARS-CoV-2 infection, the diagnosis has to be at least 90 days prior to study randomization. If previously diagnosed, previous treatment with Ivermectin or hydroxychloroquine is acceptable.
- Have a negative SARS-CoV-2 antigen rapid test performed in the office at screening
- Patient willing to receive treatment with AZD7442 600 mg IM or IV
- Patient willing to complete baseline and 14 post-enrollment Patient Experience/Clinical Outcome Assessment surveys.
- Patient willing to complete baseline (Day 2) and 5 follow-up QoL assessments
- Patient willing to have blood drawn for serum concentration of AZD7442 5 times post-baseline and repeated if patient becomes COVID-19 positive
- Patient willing to have blood drawn for T-cell assay at day 30 and at day 210 post-baseline and repeated if patient becomes SARS-COV-2 RNA by RT-PCR positive
- Patient willing to have RBD-IgG drawn at baseline, days 90, 180, 270 and 360 post-baseline and repeated if patient becomes SARS-COV-2 RNA by RT-PCR positive
- Patient willing to signed Informed Consent Form
- Patient willing to sign Authorization for Release of Health Information (including treating physicians' or other medical personnel's records, medication prescriber records, pharmacy records and medical insurance claims)

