9.3 Follow-Up Activities

Follow-Up activities are as follows:

- At Day 180 post-baseline, all patients will be administered a repeat dose of AZD7442 600 mg IM or IV. The window for this treatment will be +/- 5 days from the actual due date. The dose will be administered in the same manner as the baseline dose unless patient circumstances require a different route of administration. All requirements listed above for baseline AZD7442 administration both IV and IM will be followed for the repeat dose including the one-hour post-dose observation period.
- Patients will complete follow-up Patient Experience/COA surveys on days 2, 30, 60, 90, 120, 150, 180, 181, 210, 240, 270, 300, 330 and 360 post-baseline at home. The window for these surveys will be +/- 5 days from the actual survey due date except for day 2 survey which is +5 days only.
*NB - Study participants will complete all surveys via mobile phone, desktop, laptop, tablet computer or via Call Center. The study site is not responsible for patient completion of the surveys.
- Patients will complete QoL assessments on days 2, 30, 90, 180, 270, and 360 post-baseline at home. The window for these assessments will be +/- 5 days from the actual due date except for day 2 assessment which is + 5 days only.
- Site personnel will obtain blood for serum concentration of AZD7442 at days 30, 90, 180, 270 and 360 post-baseline in the office for all patients. The window for these blood draws will be +/- 5 days from the actual due date. All

serum concentration measurements will be sent to PPD Bioanalytical Laboratory in Richmond, VA for analysis.

- Site personnel will obtain blood for RBD-IgG antibody level at days 90, 180, 270 and 360 post-baseline in the office for all patients. The window for these blood draws will be +/- 5 days from the actual due date. All RBD-IgG antibody levels will be sent to LabCorp for analysis.
- Site personnel will obtain blood for T-cell assay at Day 30 post-baseline in the office for all patients and send to Isoplexis in Branford, CT for analysis. A subset of patients will be selected including 120 patients with hematologic malignancy and 60 patients with solid tumors in order to have site personnel obtain blood for repeat T-cell assay at Day 210 post-baseline in the office and send to Isoplexis in Branford, CT for analysis. The window for these blood draws will be +/- 5 days from the actual due date.

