14.2 Secondary Endpoint Analysis

All secondary endpoints will be analyzed for the Intent-To-Treat (ITT) population with a Per-Protocol (PP) sensitivity analysis.

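### The 'ITT' set is defined by post-dose survival and completed assessments, yet it carries the infection, death and time-to-event comparisons

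*Protocol*

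**What the plan says.** Protocol section 17.4 fixes the analysis sets: "The study will analyze two populations as defined by Intent-To-Treat (ITT) and Per Protocol (PP) criteria". No all-treated set is named. Besides dosing and the baseline items, ITT membership requires that the patient "complete at least one serum concentration AZD7442 measurement post-baseline AZD7442 administration", and then "one RBD-IgG post-baseline, complete the Day 30 T-Cell assay, complete at least one follow-up Patient Experience/COA survey and one QoL assessment". The baseline QoL form that ITT also requires is completed on Day 2 (sections 8.1 and 19.1), so it too is collected after dosing.

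On timing, section 9.3 states: "Site personnel will obtain blood for RBD-IgG antibody level at days 90, 180, 270 and 360 post-baseline in the office for all patients". The T-cell assay and the first concentration are due on Day 30. For the draws: "The window for these blood draws will be +/- 5 days from the actual due date".

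On use of the set, section 14.2 states: "All secondary endpoints will be analyzed for the Intent-To-Treat (ITT) population with a Per-Protocol (PP) sensitivity analysis". Section 17.6 repeats this. Section 17.9 assigns the rate of symptomatic infection including hospitalization and death, the adverse event rate and (if information suffices) the death rate to ITT, again with per-protocol as sensitivity. Time to first event, with death among the events, is a secondary endpoint in section 14.1. The primary concentration endpoint is analysed in both sets (section 13.2).

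**The concern.** An intention-to-treat set should be fixed by what is known at or before treatment. Here membership depends on being alive, still in the study and compliant for weeks to months after dosing, while the outcomes are infection, hospitalization and death over that same period. Patients who remain have death-free time built in (immortal time).

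The conditions are also not needed for these outcomes. Section 17.5 determines infection from RT-PCR, the medical record or claims, none of which requires a T-cell result or a QoL form. For the primary endpoint, a patient with usable concentrations at every visit is dropped if the Day 30 T-cell assay was missed.

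At stake are the first-listed secondary comparisons (solid tumor against hematologic malignancy, and the four therapy strata), the time-to-event analysis and the reported death rate.

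**Working it through.** The protocol states no figure for exclusions from ITT, so there is none to reproduce. The check traces the criteria against the schedule and then sizes the exposed window.

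**1. Earliest dates at which the criteria can be met** (sections 9.3 and 17.4)
- T-cell assay and first scheduled concentration: 30 − 5 = Day 25.
- First scheduled post-baseline RBD-IgG: 90 − 5 = Day 85.
- Unscheduled RBD-IgG: in the office, about 10 days after a positive RT-PCR or when return is safe. It can meet the RBD-IgG criterion before Day 85. It does not replace the Day 30 T-cell assay.

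**2. Who is out**
- Death or withdrawal before about Day 25: always.
- Day 30 T-cell assay missed for any reason: always.
- Death or withdrawal between about Day 25 and Day 85: out unless the unscheduled RBD-IgG was drawn.
- Early hospitalization: out only if it leads to death, withdrawal or a missed Day 30 assay. The RBD-IgG criterion has no deadline, so a draw at Day 90, 180, 270 or 360 satisfies it.

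**3. Share of 12-month deaths** (assumption: constant hazard over 360 days)
- Always excluded: 25/360 = 6.9%.
- Possibly excluded: up to 85/360 = 23.6%.

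**4. Number of SARS-CoV-2 related deaths** (assumption: 12-month risk of 1% to 5%; n = 1,500)

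| Assumed risk | Deaths | Before Day 25 | Before Day 85 |
|---|---|---|---|
| 1% | 1,500 × 0.01 = 15 | 15 × 0.069 ≈ 1 | 15 × 0.236 ≈ 4 |
| 5% | 1,500 × 0.05 = 75 | 75 × 0.069 ≈ 5 | 75 × 0.236 ≈ 18 |

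**5. Direction.** Let p be the true risk, f the share of event patients lost and q the share of event-free patients lost. The risk seen in ITT is p(1−f) / [p(1−f) + (1−p)(1−q)], which is below p when f > q and above p when q > f.
- Death: early deaths are removed by construction, on top of any loss that affects everyone. So f > q unless missed assessments fall mainly on patients who would survive.
- Infection: an infected patient who recovers can stay in, while uninfected patients who withdraw or die of cancer leave the denominator. Either sign is possible.

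**6. Solid against hematologic comparison** (illustration; assumed true risks 4% hematologic, n = 300, and 2% solid, n = 1,200; q = 0)
- 24% of event patients lost in both: 9.12/297.12 = 3.07% against 18.24/1,194.24 = 1.53%. The ratio stays near 2.0, but both risks fall by about a quarter.
- 40% lost in hematologic, 24% in solid: 7.2/295.2 = 2.44% against 1.53%. The ratio falls to 1.6.
- 24% lost in hematologic, 40% in solid: 3.07% against 14.4/1,190.4 = 1.21%. The ratio rises to about 2.5.

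**7. Does per-protocol help?** It also requires the Day 210 T-cell assay, which section 9.3 schedules only for 120 hematologic and 60 solid tumor patients. Read literally, it holds at most 120 + 60 = 180 of 1,500, selected harder still.

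**The case against.** The best defence is that the events are not lost to the trial. Section 17.10 describes all patients with symptomatic breakthrough infection, section 18.1 words safety for all qualified treated patients, and every death is an SAE (section 25.13.5). This stands, but these are descriptions and reports. The planned between-group comparisons remain in ITT.

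Second, the primary endpoint is serum concentration, which needs a post-dose sample anyway. This stands for that one condition and does not justify the other four.

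Third, the constant hazard may overstate early deaths. Section 8.2 excludes ECOG 2 or higher and expected survival under 12 months, and section 2.1 allows breakthrough risk to vary with time since dosing. This stands as a caution on the percentages.

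A reader might also infer more than the protocol supports:
- That every early hospitalization drops out. It does not (step 2).
- That the baseline antibody test removes treated patients. Section 5.2 specifies "RBD-IgG antibody testing in all vaccinated participants who are at least 4 weeks post their most recent vaccine dose", while section 8.1 admits patients vaccinated with a "COVID-19 vaccine at least 14 days prior to Baseline". That is a scheduling inconsistency. Under section 9.1 the blood is drawn before the patient proceeds to the baseline visit, so a patient treated per protocol has a sample.
- That mainly hematologic patients are lost. Hematologic patients in remission may enter up to 12 months after treatment, whereas solid tumor patients who are stable or in remission are limited to 6. The protocol does not show which cohort loses more.
- That infection incidence is certainly understated. Step 5 shows that it need not be.
- That the loss should be counted in all-cause deaths, or that laboratory failures add a known number. The secondary endpoints concern SARS-CoV-2 related death. The protocol gives no T-cell failure rate and does not say whether a drawn sample that fails in the laboratory counts as incomplete.

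**Conclusion.** The defect is structural and holds at any event rate: the set called ITT is selected on survival and compliance after treatment, and the only sensitivity set is selected harder. Followed as written, the plan biases death and time-to-death results downward and exposes infection incidence to selection bias of unknown sign. It distorts the solid against hematologic comparison if loss differs between cohorts, in a direction that cannot be derived from the protocol.

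The certain part is about 7% of 12-month deaths and the upper limit about 24%, or about 1 to 5 and up to about 4 to 18 SARS-CoV-2 related deaths. These figures rest on the assumed constant hazard and the assumed 1% to 5% risk. The number lost through missed Day 30 assays cannot be derived. This should be corrected before analysis.

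**What to change.** In section 17.4, define the main set as all enrolled patients who received any AZD7442, and name it in sections 14.2, 17.6 and 17.9 for infection, hospitalization, death, time-to-event and safety analyses. For the concentration endpoint, use all treated patients with at least one post-dose concentration. Apply the T-cell, RBD-IgG, survey and QoL conditions only to analyses that use those data.

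The cost is wording; no new data collection is needed. The small downside is more patients with incomplete covariates in the correlation analyses.
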